14.1 Study Medication Description (from Pfizer, Inc.)

Azithromycin

Zithromax® for oral suspension is supplied in bottles containing azithromycin dehydrate powder equivalent to 1200mg per bottle and the following inactive ingredients: sucrose; tribasic anhydrous sodium phosphate; hydroxypropyl cellulose; xanthan gum; FD&C Red #40; and flavoring including spray dried artificial cherry, crème de vanilla, and banana. After constitution, a 5mL suspension contains 200mg of azithromycin.

14.1 Dosage Information

Azithromycin and placebo will be administered as a single dose, in oral suspension form for children. Dosing will follow the WHO recommendations for treatment of active trachoma:

- Single dose of 20mg/kg in children (up to the maximum adult dose of 1g)
- Height-based dosing of children (this dosing method is supported by the WHO)

Individuals who are allergic to macrolides/azalides will not be treated.

14.2 Medication Procurement/Donation

Azithromycin (Zithromax®) and the placebo have been donated by the Pfizer Corporation. There will be no costs to acquiring the study medication. Pfizer, Inc. will ship azithromycin and placebo directly to the study sites.

Representatives of each study site will manage the customs process and transport the medication from the port to storage sites.

14.3 Medication Quality Control

Study medication will be stored at each country site prior to use. The study coordinator and other local staff will regularly check and record the study medication expiration dates. The expiration dates on the medication containers will be strictly monitored and all expired study medicine will be discarded appropriately.

14.4 Antibiotic Distribution & Monitoring Coverage

After the MORDOR 0 census and monitoring/collection is complete, treatment (azithromycin and placebo) will be administered to all eligible community members per study protocol. Teams will participate in training exercises regarding drug/placebo distribution and recording techniques prior to each treatment cycle. Training will be in accordance with the Zithromax Program Manager's Guide from the International Trachoma Initiative.

During mass drug administration, distribution team members will use tablet computers equipped with an electronic data capture system to seek out each eligible child on the census, administer antibiotic or placebo, and record whether or not each person has been treated. The distribution team will document individual reasons for not being treated (e.g. death, temporary absence, permanent migration, refusal of treatment, etc.). Consumption of medication will be directly observed and the dose distributed will be documented in the electronic data capture system.

We will estimate antibiotic coverage from the most recent biannual census records, aiming for treatment of 80% of children. At the end of each treatment round, the UCSF DCC will identify any children who have missed 2 or more consecutive treatments, and forward this information to the site study coordinator. Census teams will discern the reason for missing treatments (including unrecorded death) at the next scheduled census. This system will serve as a quality control mechanism to reduce the number of false negative deaths in the study.

14.5 Adverse Reactions/Side Effects

Azithromycin is generally well-tolerated. The most common side effects of azithromycin are diarrhea, nausea, abdominal pain, and vomiting, each of which may occur in fewer than one in twenty persons who receive azithromycin. Rarer side effects include abnormal liver function tests, allergic reactions, and nervousness. Diarrhea due to *Clostridium difficile* has been reported in rare cases.

During the consent process, the common adverse reactions that may occur will be explained to parents/guardians and they will be advised to communicate adverse events to local program representatives immediately. If, for any reason,

the participant needs further care, they will be referred to the nearest health center for examination and treatment.

The trial sites will be masked to outcomes, so the responsibility for monitoring interim analysis will fall on the DSMC. Statistical monitoring is discussed in the Statistical Analysis Plan. The Data Safety and Monitoring Committee (DSMC) will be given authority to discontinue treatments at any time if there is evidence of unexpected harm.

14.6 Adverse Events Systems

Both active and passive monitoring systems for adverse events are in place for this study, and these monitoring activities will specifically include (but will not be limited to) treated 1-6 month olds. We will monitor adverse events following mass treatments actively at each follow-up census and during a house-to-house survey of all 1-6 month olds in a random selection of azithromycin and control communities.

14.6.1 Passive Adverse Events Monitoring

We will implement a passive monitoring system during the treatment phase, by instructing parents to report any adverse events in the two weeks following each mass azithromycin distribution to a local healthcare provider. Children will be referred for follow up care on a case-by-case basis.

14.6.2 Active Adverse Events Monitoring

During Census

We will employ two forms of active monitoring for adverse events. First, during each follow-up census we will ask the guardians of all 7-12 month-old children in all study communities (both mortality and morbidity), whether their children had an adverse event after the previous mass medication distribution. This will allow assessment of adverse events from medication distribution among the individuals aged 1-6 months at the time of the distribution. This information will be incorporated into the electronic data capture system so that this question is asked for any child aged 7-12 months. Note that this method will be subject to recall bias, so we will also perform a house-to-house survey (described below).

Infant Adverse Events Survey

To identify any adverse events associated with mass treatment, the UCSF DCC will randomly select 30 study communities (15 azithromycin and 15 control communities) to participate in an adverse events survey. This survey will be performed by the census workers masked to treatment arm, approximately 2 weeks after a mass medication distribution. During the survey, adverse events will be elicited only for study participants aged 1-6 months at the previous census. A structured questionnaire will be performed to elicit dangerous side effects, followed by an open-ended question. Specifically, we will ask the primary caregiver about the following symptoms during the time since the previous antibiotic distribution: abdominal pain, vomiting, nausea, diarrhea, dyspepsia, constipation, hemorrhoids or rash. To elicit symptoms of serious infantile hypertrophic pyloric stenosis which has been reported in rare occasions with macrolide use, census workers will be trained to ask about projectile vomiting and feeding problems.

Training

The household survey team will be the same individuals who conducted the census. They will be trained in survey administration methods, including:

1. Obtaining informed consent
2. Accurately selecting the appropriate households to interview
3. Remaining neutral when asking questions (i.e. asking the question exactly as it is written on the paper in a neutral tone of voice, so as not to lead the respondent or introduce bias)

Serious Adverse Events

Any serious adverse events (SAE) will be reported to Pfizer. An **IIR SAE Form** (*Investigator-Initiated Research Serious Adverse Events Form*) will be completed for each event. (See Appendix for form and complete instructions.)

According to Pfizer, an SAE is any adverse event that:

- Results in death
- Is life-threatening (i.e., causes an immediate risk of death)
- Requires inpatient hospitalization or prolongation of existing hospitalization
- Results in persistent or significant disability or incapacity
- Results in a congenital anomaly or birth defect

Or that is considered to be:

- An important medical event

All community residents will be advised to alert a village health worker if they experience, within one week of mass treatment, a serious adverse event (by the preceding definition). An SAE report must be submitted for all deaths in the study – regardless of the time of treatment. The local health worker will report to the on-site study coordinator; who must, within 24 hours, submit a Pfizer **IIR SAE Form** to [contact]. TL will review, and forward to Pfizer and/or the Medical Monitor, as appropriate. SAEs must be submitted to Pfizer within 24 hours of receipt from the on-site coordinator. TL will also forward SAE to DSMC if meets criteria of being possibly related to study drug.

Deaths that are reported to the study team outside of the biannual census (primary outcome) will be reported as an SAE to Pfizer. Note that deaths identified via the biannual census, which constitute the primary outcome, will not be reported as SAEs. Deaths that are reported to the study team as part of the biannual census will be reported to Pfizer in aggregate, not by arm, on a quarterly basis.

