6.1. Census

Census Team

Census workers will be selected by the site study coordinator. These individuals may have different qualifications and educational backgrounds in the 3 sites, but, at a minimum, each census team member should be computer-literate, such that they are able to operate a tablet computer and type on its keyboard. Census workers will ideally be local community dwellers, and familiar with the communities being enumerated. In addition, several supervisors will be present for the duration of the census to monitor census workers.

Census Training

Census workers will be trained at the beginning of the study and refresher trainings will be offered as needed for the duration of the study. Training will start with reviewing the census data collection software on the tablet computer, care of the tablets, charging of the tablets, etc. The training will then proceed to a demonstration of the use of the software at a mock household, including common problems that staff may encounter (e.g., no one at home, GPS function not working, software crashing). In the final part of the training, the study coordinators and investigators will accompany team members to several communities and observe the census activities.

Census Software

The census will be directly entered into a tablet computer. The software will capture information about each child aged 0-5 (or 0-12 in morbidity communities) in each household: name, age, sex, father's name, and mother's name, and will also register any pregnant women. The GPS coordinates will be documented for each household at the entrance to the household. At follow-up

censuses, team members will identify each household on the existing census, and will update the status for each child:

- STATUS: Alive, slept in household last night
- STATUS: Alive, but not in household
 - o ABSENCE: <1 month
 - Is he/she coming back within 1 week?
 - Yes (mop-up)
 - No
 - I don't know
 - INFORMANT: household member, neighbor, village chief, other
 - o ABSENCE: \geq 1 month
 - MOVE: Moved within community
 - INFORMANT: household member, neighbor, village chief, other
 - MOVE: Moved outside of community
 - INFORMANT: household member, neighbor, village chief, other
- STATUS: Died
 - o PLACE: Child living in community when died
 - INFORMANT: household member, neighbor, village chief, other
 - o PLACE: Child had moved out of community when died
 - INFORMANT: household member, neighbor, village chief, other
- STATUS: Unknown

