6.3. Verbal Autopsy

Verbal autopsy questionnaires will be completed for all deceased children (aged 1-60 months).

Staff

Verbal autopsy interviews will be conducted by trained staff. Training will focus on conducting sensitive interviews with persons who may still be in mourning; discussion of verbal autopsy questions; reviewing the format of the paper and/or electronic questionnaires (including skip logic); and demonstration of the verbal autopsy technique on 5 mock deaths. The 5 first verbal autopsies will be observed by the study coordinator to ensure that proper procedures are followed. Each verbal autopsy interviewer will be responsible for a distinct geographic area, and will be responsible for regular contact with the key informant from each community.

Identification of Deaths

Deaths will be identified in 2 ways: from the biannual census, and from the key informant system. The trial biostatistician will provide a list of all deaths to the site study coordinator after each census. This list will include information on the deceased child's name, age, gender, and unique identification number; community name; and father's and mother's names. The study coordinator will in turn deliver this list to the appropriate verbal autopsy interviewer. The verbal autopsy interviewer will also keep a record of all deaths identified by the key informants. In each case, the key informant will report the community name, child's name, and parents' names, and the deceased child will be located in the census database.

Questionnaire Administration

Each site will choose between the full-length WHO questionnaire (2007 version) or an abbreviated form (which utilizes questions from both WHO 2007 and 2012), translated into the local language as appropriate. Questionnaires will be administered at the home of the deceased child. The informant will be the deceased child's parent or guardian. If this person is not available, the verbal autopsy interviewer will try to arrange a time to return to interview this person. If the parent or guardian is not present on the third visit, they will complete the questionnaire by interviewing another family member, or as a last resort, a neighbor. All interviews will be completed in the local language. Our goal is to perform each verbal autopsy within 2 months of identification of death. The child's name and unique identification number will be recorded on the verbal autopsy record for identification purposes.

Assigning the Cause of Death

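### The census adverse-event question reaches only infants who survive to the next census, so a fatal reaction first learned of there has no specified adverse-event record

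*Protocol*

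**What the plan says.** Protocol section 14.6.2 (During Census) puts the question to guardians in all mortality and morbidity communities and builds it into the data capture system "so that this question is asked for any child aged 7-12 months". The stated purpose is wider: "This will allow assessment of adverse events from medication distribution among the individuals aged 1-6 months at the time of the distribution". One weakness is acknowledged: "Note that this method will be subject to recall bias, so we will also perform a house-to-house survey".

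Section 6.1 lists what the census software records for a child whose status is died: the place (for example "Child living in community when died") and the informant. Section 10.2 adds dates of death. Neither lists an adverse-event item.

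Under Serious Adverse Events, section 14.6.2 says that "deaths identified via the biannual census, which constitute the primary outcome, will not be reported as SAEs", and that such deaths "will be reported to Pfizer in aggregate, not by arm, on a quarterly basis". The same subsection also requires an SAE report for every death in the study, whenever treatment was given.

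Section 6.3 says: "Verbal autopsy questionnaires will be completed for all deceased children" (aged 1-60 months).

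**The concern.** The population asked and the population described are not the same. The protocol describes infants aged 1-6 months at distribution; the rule selects children aged 7-12 months at the next census. The difference is the infants who died or left in between, and those who died include anyone with a fatal reaction to the dose.

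This matters because infants of 1-6 months are the group singled out for safety. Section 14.6.3 promises their side effects separately, and section 14.6.2 names a serious infant condition that the infant survey should look for. The census question is the only active adverse-event system that covers every community. Its by-arm result is conditioned on survival, which is the outcome the drug is meant to change. The house-to-house survey is offered as the remedy for recall, not for survivorship.

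**Working it through.** **1. Age rule.** With six months between distribution and census, the window 1-6 months becomes 1 + 6 = 7 to 6 + 6 = 12 months. The rule is therefore correct for a child who is still alive. A child who has died is not aged 7-12 months at the census. That dead infants are left out is an inference from the age rule and the listed fields; the protocol does not say so in words, but nothing in its text contradicts it.

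**2. Path of an infant dosed at 1-6 months who reacts and dies, where the study first hears of it at the census.**
- Census adverse-event question: not triggered.
- Census fields for a dead child: place and informant (section 6.1) and date of death (section 10.2).
- SAE form: excluded by one sentence of section 14.6.2 and required by another.
- DSMC: section 14.6.2 forwards an SAE judged possibly related to the drug. Without an individual SAE form, no step is described at which that judgement would be made.
- Verbal autopsy: held, but the body of the protocol does not say that it asks about events after the dose. The questionnaire is listed in the Appendix and was not in the text reviewed.

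**3. Scale.** The documents state no figure to reproduce. The inputs are from SAP Study A item 1: 668 people per community, 17% in the age range, 312 communities per arm, and death rates of 2% and 2.5% per year. An even spread over the 59 months of eligible age is an assumption.
- Infants aged 1-6 months per community: 668 × 0.17 × 6/59 = 11.5.
- Per arm: 11.5486 × 312 = 3,603, or about 3,600.
- All-cause deaths in six months: 3,603 × 0.01 = 36 to 3,603 × 0.0125 = 45 per arm.
- If infant mortality is double the all-age rate (assumption): 3,603 × 0.02 = 72 to 3,603 × 0.025 = 90.
- At the 80% coverage aim in Protocol section 14.4, with equal mortality in treated and untreated infants (assumption): 36 × 0.8 = 29 to 45 × 0.8 = 36 at the stated rates.

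These are deaths for which the question is not asked. They are not reactions.

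**4. Can the two-week survey fill the gap?** It takes 15 communities per arm, so 15 × 11.5 = about 173 infants. Expected deaths in two weeks are 173 × 0.02 × 2/52 = 0.13 to 173 × 0.025 × 2/52 = 0.17 per arm. It is too small to show fatal reactions by arm.

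**5. Effect on common mild events.** At 1% six-month mortality in one arm and a 20% reduction in the other, survivors are 99.0% and 99.2%. Those denominators are almost equal, so rates of common mild events hardly move. What can be lost is rare severe events.

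**The case against.** A reader might infer that an infant who reacts and dies is absent from all adverse-event data, so that the whole by-arm safety comparison is made among survivors. The documents do not support that. Several routes do not depend on survival to the census:
- parents are told to report events within two weeks (section 14.6.1);
- residents alert a village health worker to an SAE within one week (section 14.6.2);
- key informants give immediate notice of sudden deaths thought to be drug-related (section 14.6.3);
- deaths learned of outside the census are filed as SAEs (section 14.6.2);
- the two-week infant survey selects by age at the previous census, not by current age, although it covers 30 communities and does not say whether caregivers of dead infants are asked.

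A reader might also infer that the mortality data cannot point to harm after dosing. That is too strong. SAP Study A item 4a compares time since treatment among deaths, including between arms, and Study B item 7 plans models of timing. Item 4b reports mortality for ages 1-5 months. The DSMC sees efficacy endpoints and adverse events by arm in its closed reports (section 17.5).

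All of this stands and narrows the point. It does not close it. The passive routes need someone to report promptly, and the key-informant route needs the drug to be suspected already. The timing analysis could show a cluster of early deaths but records no symptoms. For the contingency study, section 17.8 plans no interim analysis and no stopping rules, so mortality monitoring is a weaker backstop there.

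A further fair objection is that bereaved guardians may recall differently from guardians of living infants, so adding their answers could introduce a bias of its own. That argues for showing the answers separately, not for leaving the question out.

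**Conclusion.** The point holds in a narrow form. As written, the census adverse-event question is conditioned on survival, contrary to the coverage claimed for it, and recall bias is the only limitation stated. A fatal reaction that first reaches the study at the census has no specified adverse-event record. The two SAE sentences in section 14.6.2 contradict each other and must be reconciled; both stand in the current text.

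The size of the loss cannot be derived. The 36-45 all-cause deaths per arm per six months rest on the SAP's Niger planning inputs, an even age spread and the all-age death rate, before treatment coverage. They bound how often the question goes unasked; they do not count missed reactions. The documents do not give the share that follow a reaction, or the share first learned of at the census. The effect on rates of common mild events is negligible. This is an inexpensive improvement to the infant safety data, not a threat to the mortality comparison.

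**What to change.** 1. Define the census question by age 1-6 months at the previous distribution instead of current age.
2. For infants in that group recorded as died, ask the guardian the same question, with date of onset, at the verbal autopsy visit already planned. First check the questionnaire and app manual in the Appendix, in case it is already asked.
3. Report these answers by arm on a line separate from survivors' answers, because recall may differ, and give rates over all infants dosed. Section 14.4 already records treatment for each child, so the denominator exists.
4. Reconcile the two sentences in section 14.6.2 on deaths as SAEs.
5. State the survivorship limitation beside the recall limitation.

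The cost is one question in an interview already held for each death, one change to the app trigger and one table line. The downside is one more sensitive question to a bereaved guardian.

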5.1. Mortality Study

5.1.1. Core Elements (Malawi, Niger, and Tanzania)

In all three study sites, we will conduct the following study activities for the mortality study:

Training

Before the baseline visit, the University of California San Francisco (UCSF) team will certify local team members at all three study sites. Standardization activities before each biannual census will consist of didactic classroom instruction and mock census activities, followed by in-field training to harmonize protocols.

Census

An enumerated population census for 0 - 60 month olds (focusing on this age group) will be conducted every 6 months by trained field workers masked to study arm, recording births, deaths, and migration of children eligible for treatment. Pregnant women will be noted at each census, to maximize inclusion of newborns on the subsequent census.

Random Census Verification

A repeat census will be conducted in a random selection of households at each study visit. Personnel will be different from the original census. This will allow us to assess whether the census team identified all births, deaths, and migratory episodes relative to the previous census.

Verbal Autopsy

Each of the study sites will perform a verbal autopsy for all children (aged 1-60 months) identified as having died during the study.³⁹

Treatment

Children aged 1-60 months on the current census will be offered weight- or height-based (<1 year weight and children who cannot stand; ≥1 year height), directly observed, oral azithromycin suspension (or oral placebo) every 6 months for 2 years as performed in trachoma programs in each of the 3 countries. Specifically, individuals are eligible on or after their one month birthday, and prior to the day of their fifth birthday.

Antibiotic Coverage Surveillance

We will estimate antibiotic coverage from the most recent biannual census records. At the end of each treatment round at months 6, 12, and 18, we will identify any children who have missed 2 or more consecutive treatments, and forward this information to the census team.

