The site study coordinator will supervise all census activities. Formal checks of census quality will be conducted through the random census verification. In addition, the study coordinator will visualize all censused households using imagery from GoogleMaps. The goal of this activity will be to minimize the chances of missing large neighborhoods or specific regions within study communities. The study coordinator will also check the data entry progress for each community, paying special attention at the follow-up censuses, as to whether there are any missing data for the “vital status” variable (i.e., present, dead, absent). Once the study coordinator is confident that the entire community has been reached, and that the amount of missing data are acceptable (defined as <10% of children in a community), the study coordinator (or other research team member) will certify the census data collection for that community complete via Salesforce. Changes can be made to the record at different time points, but these changes will not be reflected until the subsequent census. All changes are time and date stamped in the database.

Census Timing

The census will be performed prior to each mass azithromycin/placebo distribution. Study sites may choose to perform the census activities over a discrete time period (e.g., all communities completed over a 1-month period, requiring census activities to take place simultaneously in many communities at once) or alternatively in a “rolling” fashion (e.g., all communities completed over a 6-month period, requiring fewer census teams to be active at once). In either case, each community must be censused every 6 months, so it may not take more than 6 months to complete all communities. The census must be completed (i.e., “locked”) at the household level before treatment can be given.

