14.6.3 Adverse Events Data

We will keep records and report all adverse events of azithromycin to the DSMC. We will report both efficacy and side effects of azithromycin separately for the 1-6 month old age group. For any “sudden deaths” believed to be associated with azithromycin treatment, key informants will immediately notify the verbal autopsy interviewer via SMS message or another appropriate form of rapid communication.

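### The census adverse-event question is triggered by current age, not age at dosing, so any delay between census and dosing skips the youngest treated infants

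*Protocol*

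**What the plan says.** Protocol section 14.6.2 describes two active adverse-event systems. The first is the census item: "we will ask the guardians of all 7-12 month-old children in all study communities", covering the mortality and morbidity communities alike, about the previous distribution. The app applies the age rule automatically, so that "this question is asked for any child aged 7-12 months". The stated rationale is: "This will allow assessment of adverse events from medication distribution among the individuals aged 1-6 months at the time of the distribution". The second system is a house-to-house survey about two weeks after a distribution, in 30 communities, limited to infants aged 1-6 months at the previous census.

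Four other provisions bear on the timing and the target group:

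- Section 5.1.1, on the lower age limit for treatment: "individuals are eligible on or after their one month birthday".
- Section 6.1, on the order of events: "The census will be performed prior to each mass azithromycin/placebo distribution".
- Section 6.1, on the interval: "each community must be censused every 6 months".
- Section 14.6.3, on reporting: "We will report both efficacy and side effects of azithromycin separately for the 1-6 month old age group".

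Section 18.1 allows for treatment being given separately from the census. Section 9.1 places swabbing in the morbidity communities between census and treatment. Section 6.1 requires the census to be locked for a household before anyone in it is treated. No section states how long the census-to-dose lag is or may be.

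**The concern.** The rule selects on age at the follow-up census, but the group of interest is defined by age at dosing. The two agree only for one value of the dose-to-census gap. The 6-month clock in section 6.1 runs from census to census and dosing comes after the census, so in a community that keeps to schedule a lag can only shorten the gap. A shorter gap removes infants from the bottom of the age range.

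The loss is not made good later. Take an infant dosed at 1.5 months and censused 5.3 months afterwards, which implies a lag of about three weeks (6 - 5.3 = 0.7 months). The child is 6.8 months old and is not asked. Six months later the child is 12.8 months old and is asked, but about the more recent distribution. The first dose is never queried.

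What is at stake is coverage of the youngest treated infants in the only active safety question put in every study community. Sections 14.6 and 14.6.3 single out this age group for monitoring and separate reporting.

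**Working it through.** **Inputs.** Target: age at dosing 1-6 completed months, i.e. [1, 7) months (14.6.2). Trigger: age at follow-up census 7-12 completed months, i.e. [7, 13) (14.6.2). Census interval: 6 months, dosing after census (6.1). Lag from census to dosing: not stated, so varied below.

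**Step 1: the mapping.** Let g be the dose-to-census gap. Age at census = age at dosing + g, so the trigger captures dosing ages [7 - g, 13 - g).

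**Step 2: reproduce the protocol's own equivalence.** At g = 6 the captured ages are [1, 7), exactly the target. At every other g the two intervals differ.

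**Step 3: the gap on schedule.** g = 6 - lag, with the lag in months (days / 30.4375).

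**Step 4: who is skipped.** For g below 6 (and at least 5 for the second formula), infants dosed at ages 1 to under 7 - g months are missed. If ages are spread evenly:

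- share of the 1 to under 7 month band missed = (6 - g)/6 = lag/6
- share of those dosed at 1 to under 2 months missed = 6 - g = lag

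| Assumed lag | Lag (months) | g (months) | Missed, whole band | Missed, dosed at 1 to <2 months |
|---|---|---|---|---|
| 0 days | 0 | 6.00 | 0% | 0% |
| 3 days | 0.099 | 5.90 | 1.6% | 10% |
| 7 days | 0.230 | 5.77 | 3.8% | 23% |
| 14 days | 0.460 | 5.54 | 7.7% | 46% |
| 30 days | 0.986 | 5.01 | 16.4% | 99% |

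Example, 14 days: 14/30.4375 = 0.460; 0.460/6 = 7.7%.

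**Step 5: the other edge.** The same shift brings in children outside the target. At g = 5.5, those dosed at 7 to under 7.5 months are asked. If a census runs late the error reverses: at g = 6.5, infants dosed at 6.5 to under 7 months are missed (0.5/6 = 8.3%) and the youngest are kept.

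**Step 6: sensitivity to the age convention.** Reading the bands as exact ages 1 to 6 and 7 to 12 still gives full capture only at g = 6. At g = 5.5 the capture is 4.5/5 = 90%, against 5.5/6 = 91.7% above.

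**The case against.** The strongest reply concerns size. No lag is stated, and locking by household permits dosing almost immediately after enumeration, in which case the loss is close to zero. Section 18.1 speaks of separate treatment only conditionally. This stands: the documents do not show that the gap usually differs from 6 months, and a reader should not infer that. They show only that the rule fails whenever there is a lag, and that a lag is allowed.

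Other mitigation also stands. The 3.8 kg minimum weight in Chapter 14 keeps some of the youngest infants out of treatment, so fewer treated infants are skipped than the age band suggests. The 30-community survey, passive reporting (14.6.1), serious-event reporting and the ascertainment of deaths do not depend on this trigger. The protocol itself concedes that the census item is open to recall bias.

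Three stronger readings are tempting and are not supported:

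- **The one-month tolerance in Table 1 moves every visit.** The asterisk is attached to the MORDOR 0 calendar window only, so it cannot be used as a per-community tolerance at each round.
- **Detection of pyloric stenosis is undermined.** The questions directed at that condition belong to the house-to-house survey, which is keyed to age at the previous census and is untouched by this rule. The size of that survey is a separate matter.
- **The reported 1-6 month group will be contaminated.** Undosed children and those dosed at 7 months or older are asked, but section 14.4 records each child's treatment status, so they can be removed at analysis. Section 14.6.3 does not say the group will be defined by the trigger age.

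**Conclusion.** The concern holds in a limited form. The equivalence in section 14.6.2 is true only at a gap of exactly 6 months, and nothing else in the documents corrects the trigger. On schedule, any census-to-dose lag skips the youngest treated infants, and those unasked infants are the only loss that analysis cannot recover.

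The size depends on a lag that the documents do not give: from almost nothing with same-visit dosing, to about 8% of the band and 46% of those dosed at 1 month of age at two weeks, and about 16% and 99% at 30 days. These figures assume an exact 6-month census interval, ages spread evenly within the band, and no allowance for the weight floor. The rule works identically in both arms, so the main cost is coverage and labelling rather than a built-in difference between arms. Severity: minor to moderate.

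**What to change.** Trigger the question on two recorded facts: the child was dosed at the previous distribution, and was under 7 months old on that dosing date. Current age should play no part. Define the 1-6 month group in the section 14.6.3 report by age at dosing.

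For rounds already collected, reclassify the responses by age at dosing. State, by arm, how many infants treated at 1-6 months and found at the follow-up census were never asked. Report the observed distribution of the dose-to-census gap, which replaces the assumed range above with a fact.

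The cost is one change of app logic. Ages or birth dates and treatment records are already captured electronically (sections 14.4 and 18.1), and the SAP's time-since-treatment analyses (Study A, supplementary analyses) presuppose dosing dates. The number of interviews stays about the same. The recall limitation that the protocol acknowledges remains. Nothing about treatment or clinical management changes.
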